We believe that it is feasible to accrue the target N of 2900 during the 18 months we have allocated for accrual. In the previous self-help cessation study (C.1.2.3), we successfully recruited 1874 smokers over 16 months. Although the current study will be limited to smokers using e-cigarettes (dual users), which is a smaller population base, it is nevertheless substantial and growing. Because all contact with participants will be by telephone, internet, and mail, we are not geographically limited. The rate of accrual is limited only by the amount of advertising, staffing levels, and logistic requirements of screening callers and processing baseline data. The tremendous response to our survey (C.1.4) indicates that we can efficiently reach large numbers of potential participants. We have a history of meeting our accrual goals, even with notoriously difficult populations that required adjustments to accrual strategies. Most notably, we have recruited participants from a much smaller segment of the population: 700 women in months 4-8 of their pregnancy who had already quit smoking and were interested in relapse-prevention assistance (Brandon et al., 2012; Lopez et al., 2008).

C.3.3. Study Arms

In this section, we describe the rationale and form of the three intervention conditions. Note that participants in both the GENERIC and eTARGET conditions will have the option of receiving electronic versions of the intervention materials via a link to a website (see C.7.2).

C.3.3.1. Assessment Only (ASSESS). Participants in this condition will not receive any intervention materials. They will participate solely in the repeated assessments. Including this comparison condition controls for the effect of repeated assessments and allows for the most meaningful evaluation of the efficacy effect size as well as the cost-effectiveness of the eTARGET intervention. This condition will also be the primary source of data for the secondary surveillance aim regarding naturalistic changes in smoking and ecigarette use over time.

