C.4.1.2. Baseline Assessment. Dual users who meet inclusion criteria and provide initial verbal consent over the telephone will be sent a bound set of baseline questionnaires or an email link to our survey site. The following questionnaires will be included: (1) a demographic and tobacco history questionnaire including the Fagerström Test for Nicotine Dependence (Heatherton et al., 1991), as well as use of pharmacotherapy and other cessation aids; (2) a questionnaire assessing current and past e-cigarette use that we developed for our recent e-cigarette survey; (3) a continuous measure of readiness to quit, the Contemplation Ladder (Biener & Abrams, 1991); (4) the Stages of Change Algorithm (SOC) (DiClemente et al., 1991); and (5) intentions to quit cigarettes and e-cigarettes. We will also assess three other motivation- related constructs: a situation-specific abstinence self-efficacy scale (Velicer et al., 1990); a recent measure of Abstinence-Related Motivational Engagement (ARME; Simmons et al., 2010), which assesses change in cessation motivation; and a measure of cigarette vs. e-cigarette outcome expectancies that we also developed for our recent survey. To test motivational mechanisms of action, these measures of motivation will be examined as potential moderator variables, with follow-up measures tested as mediators of treatment effects. Finally, we will use 1-item questions to assess overall "commitment" to, and "confidence" about being smoke-free, and 2 questions to assess craving for cigarette smoking.

Inclusion criteria will be evaluated using responses to baseline survey items. Given that participants provided responses during the initial telephone contact that met the inclusion criteria, we created rules for 4 of the 5 inclusion criteria that required strong evidence from the baseline survey for exclusion. The rules acknowledge that participants may mark unintended responses.

Those with the following responses will be excluded based on **Criterion #1** (smoking \geq 1 tobacco cigarette/week over the past year).

- Rule 1) Marked either '1-5 days a month' or 'No use in the past month' to item 4 in the 'Tobacco Cigarettes' section.
- Rule 2) Marked the designated answer to any two or more of the following in the 'Tobacco Cigarette' section: a) Item 4a: response of 7 or more days since last cigarette;
 - b) Item 5: response of 'no use in the past month'; c) Item 7: response of 'I do not smoke';

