C.4.1.3. Follow-Up Assessments. Participants will be sent follow-up assessments (by mail or email link) at 3-month intervals through 24 months, as indicated in Table 3. The length of the follow-up (24 months post-enrollment) was calculated by adding the standard 6 months after the end of the eTARGET intervention. We deliberately keep each follow-up assessment brief to minimize participant burden and consequent attrition. Each of these follow-ups will include an assessment of the use of tobacco products, e-cigarettes, pharmacotherapies, and other tobacco cessation aides or services since the previous contact. These data will constitute the Abbreviated Follow-Ups, and will be sufficient for calculating treatment outcomes as well as for the longitudinal tracking of cigarette and e-cigarette usage for the secondary aim. Full Follow-Ups at 6, 12, 18, and 24 months will include most of the questionnaires from the baseline assessment, as well as additional domains, including evaluation of the intervention (Client Satisfaction Questionnaire; Attkisson & Greenfield, 1994), self-reported use of the material (i.e., how much they read, how often they refer back, how much it affected their behavior), current intentions to guit smoking and to guit e- cigarettes, and the three motivationrelated scales administered at baseline. The 24 month follow-up will also include an 12-item measure of health outcomes (SF-12[™] Health Survey; Ware, J E, Kosinski, M, Keller, S D., 1995), 2001). Research staff will attempt to contact participants to complete any missing data on the completed baseline and follow-up assessments.

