C.6.4.2. Specific Aim 2. Generalized estimating equations (GEE) will be used to fit populationaveraged models to handle the longitudinally measured binary outcomes, with the main covariates of intervention conditions, time (months from baseline), and the interaction of condition and time. Potential confounding variables (e.g., group differences in demographic, smoking history, or pharmacotherapy use) that appear despite randomization will be adjusted for in the model. Pair-wise condition and time interval comparisons will be tested using the generalized score statistics from GEE models by utilizing the contrast statements. Further, the generalized linear mixed effects models with a logit link function will be expanded, including the participant-specific intercept and slopes as the random effects in the model. Moderators (e.g., gender, SES, quitting motivation, nicotine dependence, magnitude of e-cigarette use, expectancies)will be tested via interactions with condition and condition x time. *Mechanisms of change associated with treatment*

will be tested (e.g., motivational measures, intervention usage, e-cigarette usage) via mediation analysis, performed using Hayes' (2009) "Indirect" macro within SAS. The approach described above will be used to evaluate the primary outcome of smoking cessation as well as the secondary outcome of e-cigarette cessation.

We will extend our analysis to lapse/recovery models using the Kaplan-Meier method with log-rank test for the stratified sub-groups (e.g., lapsed and recovered groups) to test the effect of intervention condition and Cox PH models controlling potential confounding variables.

To capture proportional shifts in cigarette vs. e-cigarette use, we will create a response variable with multiple levels for each follow-up assessment reflecting the relative level of e-cigarette to cigarette use, referenced against baseline use of each product. The multi-level outcome variable will be fitted using a logistic analysis on the generalized logits to test if the interventions have a significant impact on these shifts.

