C.7.2. Printed versus internet-based materials. In theory, an internet-based intervention offers some substantial advantages: no printing or mailing costs; constant availability; and ease of distribution. However, there are also some advantages of traditional printed materials: potentially greater salience and retrievability of a tangible product: use and portability not dependent on technology; and less affected by economic barriers that may limit internet access. Because our previous efficacy studies that produced strong findings used printed materials, we are hesitant to make a wholesale shift to internet-based content. Doing so would impair our ability to interpret a failure to replicate the previous results. However, we recognize the potential advantages of internet-based delivery of health promotion content. Therefore, for the proposed study we will offer participants the option of also receiving an email with a personalized link to the appropriate booklet and to all earlier booklets in the series. They will receive this email an average of 2-3 days before they receive the printed booklets by US mail. We will collect metadata regarding use of the internet-based documents, namely how many times the link was accessed, and whether the electronic booklet(s) were downloaded, which will allow us to document their use and acceptability. We will also collect evaluations and preferences regarding internet distribution at follow-up to test as potential moderators or mediators of treatment effects. This information should assist us in deciding whether to transition fully to internet-based or mobile content (i.e., smart-phone/tablet apps) distribution in the future.

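### Opinions on internet delivery collected only at follow-up should not be tested as moderators: they post-date randomisation, and the interaction cannot be estimated against ASSESS

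*Combined protocol and SAP*

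**What the plan says.** C.7.2 (printed versus internet-based materials) describes the optional emailed link and the recording of link access and downloads, then adds: "We will also collect evaluations and preferences regarding internet distribution at follow-up to test as potential moderators or mediators of treatment effects".

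Four other places bear on that sentence.

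- **Who has electronic materials.** C.3.3 says that "participants in both the GENERIC and eTARGET conditions will have the option of receiving electronic versions of the intervention materials via a link". For ASSESS, C.3.3.1 says: "Participants in this condition will not receive any intervention materials".
- **How moderators are tested.** Under C.6.4.2 they "will be tested via interactions with condition and condition x time". There is no restriction to the two booklet arms.
- **The rule for the motivation scales.** C.4.1.2 says that "these measures of motivation will be examined as potential moderator variables, with follow-up measures tested as mediators of treatment effects".
- **When opinions of the intervention are asked.** C.4.1.3 lists "evaluation of the intervention (Client Satisfaction Questionnaire" among the domains added at the full follow-ups (6, 12, 18 and 24 months). The baseline battery in C.4.1.2 contains no item on preferred delivery format.

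**The concern.** A moderator analysis asks whether the treatment effect differs between kinds of participant who existed before treatment. Randomisation protects that question only if the grouping variable could not have been altered by allocation or by the outcome. An opinion given at 6 months or later can be altered by both: by which booklets arrived, and by whether the person has stopped smoking. Grouping by it compares sets of people whom randomisation did not balance.

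There is also a question of meaning. Someone in ASSESS has had no booklet, printed or electronic, to evaluate. A condition-by-opinion term fitted across all three arms, as C.6.4.2 would have it, therefore has no content in one of them.

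At stake is a secondary message: whether the booklets work better for people who favour one delivery route. C.7.2 lists this among the information meant to help decide on moving delivery wholly online, and C.6.3 leaves secondary and exploratory analyses unadjusted for multiplicity.

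**Working it through.** **Arm sizes (C.6.2).** The plan needs 413, 826 and 826 analysed, 2065 in all, and expects 27.5% attrition. Inflating, 2065/(1 − 0.275) = 2849 against the stated 2900, which is 1.8% apart, so the figure reproduces. The check below uses 826 per booklet arm and the planned 18-month abstinence of 20% (GENERIC) and 25% (eTARGET).

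**Estimability against ASSESS.** Write M for a favourable opinion (1) or not (0), and G and E for the two booklet arms. The three-arm model has six columns: intercept, G, E, M, G×M, E×M.

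- If ASSESS is coded M = 0, then M = G×M + E×M, and the rank is 5 of 6.
- If ASSESS is left missing, 2900 − 580 = 2320 participants remain. Then G + E = 1 as well, and the rank is 4 of 6.

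The interaction for eTARGET versus ASSESS is the effect of M in eTARGET minus the effect of M in ASSESS. The second term needs ASSESS participants at both values of M, and there are none. GENERIC versus ASSESS fails in the same way. Only eTARGET versus GENERIC remains.

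**When a false interaction appears in eTARGET versus GENERIC.** Within an arm, the odds ratio between opinion and abstinence is the same whichever is treated as the outcome. So the interaction on the odds-ratio scale equals

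(opinion–abstinence odds ratio in eTARGET) / (same odds ratio in GENERIC).

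If the two are equal the ratio is 1, and there is no logit-scale interaction.

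Worked case with assumed associations and a true effect of 5 points that no prior characteristic modifies. The log-odds of a favourable opinion are −0.2 in non-quitters (probability 0.4502), 0.5 in GENERIC quitters (0.6225) and 1.2 in eTARGET quitters (0.7685). The odds ratios are e^0.7 = 2.01 and e^1.4 = 4.06.

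- Favourable, GENERIC: 0.20×0.6225/(0.20×0.6225 + 0.80×0.4502) = 25.69%. eTARGET: 0.25×0.7685/(0.25×0.7685 + 0.75×0.4502) = 36.27%. Difference +10.6 points.
- Unfavourable, GENERIC: 0.20×0.3775/(0.20×0.3775 + 0.80×0.5498) = 14.65%. eTARGET: 0.25×0.2315/(0.25×0.2315 + 0.75×0.5498) = 12.31%. Difference −2.3 points.

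Simulation: 826 per arm, 4000 runs, two-sided 5% interaction test, same constant 5-point effect. All associations are assumptions.

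| Opinion–abstinence odds ratio, GENERIC / eTARGET | Odds ratio of arm on opinion | Rejects, logit | Rejects, risk difference | Effect if favourable | Effect if not |
|---|---|---|---|---|---|
| 1.0 / 1.0 | 1.65 | 5.4% | 5.6% | 5.0 | 5.0 |
| 2.0 / 2.0 | 1.0 | 4.6% | 7.4% | 5.8 | 3.9 |
| 2.0 / 2.0 | 1.65 | 4.6% | 6.0% | 4.0 | 2.7 |
| 3.0 / 3.0 | 1.65 | 4.9% | 7.1% | 3.4 | 1.8 |
| 2.0 / 2.9 | 1.0 | 27.8% | 47.6% | 8.4 | 0.8 |
| 2.0 / 2.9 | 1.65 | 25.8% | 38.4% | 5.9 | −0.8 |
| 2.0 / 4.1 | 1.0 | 78.5% | 90.2% | 10.6 | −2.3 |
| 2.0 / 4.1 | 1.65 | 73.0% | 80.8% | 7.3 | −3.9 |

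If opinion reflects only underlying prognosis and arm, with no direct link to quitting, rejection is 4.5 to 7.7% over the two scales (2000 runs). Even with equal associations, the effects shown within opinion groups can drift from the true 5 points, for example to 3.4 and 1.8.

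**Same test with the preference asked before randomisation.** Rejection is 4.9% (logit) and 4.6% (risk difference), and the effect is 5.0 points in both groups.

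**The case against.** The strongest defence is that C.7.2 says moderators or mediators. Follow-up timing suits a mediator, and C.4.1.2 shows that the authors know the difference. The sentence sits under design considerations rather than in the analysis plan, and delivery opinion is not among the moderators named in Specific Aim 2 or C.6.4.2. The booklet arms have the same electronic option and matched contact, so there is no stated reason why opinions of the delivery channel should relate to quitting differently in the two. No passage expressly plans a delivery moderator against ASSESS. All of this stands, and it limits the point to a small exploratory analysis. It does not rescue the moderator use, which the sentence allows.

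Four stronger readings are tempting, and the documents do not support them.

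- *A false interaction is to be expected, and large.* Striking examples are easy to build. Suppose 80% of quitters in each arm are favourable, against 40% of GENERIC and 60% of eTARGET non-quitters. That fixes odds ratios of (0.8/0.2)/(0.4/0.6) = 6.0 and (0.8/0.2)/(0.6/0.4) = 2.67, and the resulting interaction only restates those inputs. Such an example also concerns ratings of the materials, whereas C.7.2 concerns internet distribution.
- *Usage as a mediator cannot be separated from arm against ASSESS.* C.6.4.2 names "motivational measures, intervention usage, e-cigarette usage" as mechanisms. Usage is zero throughout ASSESS but varies within the booklet arm, so a model with intercept, arm and usage has full rank. With 413 ASSESS participants at zero and 826 eTARGET participants at an assumed 0 to 10, it has rank 3 of 3. Over 500 simulated trials it recovered both coefficients (arm: true 0, estimate −0.02; usage: true 0.12, estimate 0.12). Only an arm-by-usage term would fail, and none is planned.
- *The move to online delivery rests on this interaction test.* C.7.2 refers to the information as a whole, including link access and downloads.
- *The primary comparison is affected.* It is not.

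**Conclusion.** The concern holds for the moderator use only. The variable is measured after randomisation, the use departs from the plan's own rule for the motivation measures, and the interaction is not estimable for either contrast with ASSESS, where 20% of the sample has no electronic delivery to evaluate. A hypothetical preference question could be put to ASSESS, but none is planned, and it would still come after randomisation.

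For eTARGET versus GENERIC the risk is conditional. The logit-scale test stays near 5% if opinion and quitting are equally associated in both arms, and goes wrong only as those associations diverge. The 26 to 79% range rests on assumed odds ratios, not on anything in the documents. This is a minor correction to an exploratory analysis, worth making because it costs almost nothing.

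**What to change.** In C.7.2, remove the moderator use of the follow-up evaluations and preferences. Suggested sense: *evaluations and preferences regarding internet delivery, collected at follow-up, will be summarised by arm in GENERIC and eTARGET, and may be examined as exploratory mediators in the eTARGET versus GENERIC contrast only.*

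If a delivery moderator is wanted, take it from before randomisation. One candidate is whether the baseline questionnaire was completed by mail or by email link (C.4.1.2), if that was recorded. It would exist in all three arms. Another is a baseline preference item for participants not yet enrolled. Both assume that allocation follows return of the baseline questionnaire, which the consent arrangement implies but the documents do not state outright.

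The planned mediation analysis of intervention usage in C.6.4.2 needs no change on this account.

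Cost: one sentence. The trial gives up a moderation result based on experienced preference. Completion mode is only a proxy for preferred format. A new baseline item would be missing for everyone already enrolled, at least the 575 whose 3-month return rates prompted the enlarged target in C.6.2, and would add slightly to an assessment load that C.4 deliberately keeps low.
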